8.2. Interim Analysis of Efficacy Outcomes

Analysis of all endpoints in support of the primary and secondary objectives will be conducted after all subjects complete the Week 26 visit but prior to the formal completion of the trial at 52 weeks.

This will include:

- Evaluate change from baseline OA pain in the target knee as assessed by the WOMAC pain subscore at Weeks 13 and 26
- Evaluate change from baseline OA function in the target knee as assessed by the WOMAC function subscore at Weeks 13 and 26
- Evaluate change from baseline OA disease activity as assessed by the Patient Global Assessment at Weeks 13 and 26
- Evaluate change from baseline in medial joint space width (JSW) as documented by X-ray of the target knee at Week 26

Additionally, endpoints in support of exploratory objectives will also be analyzed, including:

- Evaluate change from baseline OA pain in the target knee as assessed by the WOMAC pain subscore at Week 4
- Evaluate change from baseline OA function in the target knee as assessed by the WOMAC function subscore at Week 4
- Evaluate change from baseline in WOMAC total score for the target knee at Weeks 4, 13 and 26
- Evaluate change from baseline OA disease activity as assessed by the Patient Global Assessment at Week 4
- Evaluate change from baseline in lateral JSW as documented by X-ray of the target knee at Week 26
- Determine the percentage of Outcome Measures in Rheumatology Clinical Trials (OMERACT)-Osteoarthritis Research Society International (OARSI) responders and “strict” responders at Weeks 4, 13 and 26
- Evaluate change from baseline OA disease activity as assessed by the Physician Global Assessment at Weeks 4, 13 and 26

8.2.1. Familywise Error Rate Control

The familywise error rate for the interim efficacy analyses will be controlled in the strong sense using the closed, fixed sequence testing method ([Dmitrienko et al 2010](#)). All hypothesis tests will be evaluated in the pre-specified sequential order that matches clinical inference from prior SM04690 studies regarding the relative therapeutic benefit of each dose. If a test fails to meet the

critical value of $\alpha = 0.05$, all subsequent tests will not be evaluated for the interim efficacy analysis and only be considered as exploratory analysis.

For this study, the pre-specified, fixed hypothesis hierarchy is:

- H1. Change in WOMAC Pain at Week 13, 0.07 mg SM04690 vs Placebo
- H2. Change in WOMAC Pain at Week 13, 0.03 mg SM04690 vs Placebo
- H3. Change in WOMAC Pain at Week 13, 0.23 mg SM04690 vs Placebo
- H4. Change in WOMAC Function at Week 13, 0.07 mg SM04690 vs Placebo
- H5. Change in WOMAC Function at Week 13, 0.03 mg SM04690 vs Placebo
- H6. Change in medial JSW at Week 26, 0.07 mg SM04690 vs Placebo
- H7. Change in medial JSW at Week 26, 0.03 mg SM04690 vs Placebo
- H8. Change in WOMAC Function at Week 13, 0.23 mg SM04690 vs Placebo
- H9. Change in medial JSW at Week 26, 0.23 mg SM04690 vs Placebo
- H10. Change in Patient Global Assessment at Week 13, 0.07 mg SM04690 vs Placebo
- H11. Change in Patient Global Assessment at Week 13, 0.03 mg SM04690 vs Placebo
- H12. Change in Patient Global Assessment at Week 13, 0.23 mg SM04690 vs Placebo
- H13. Change in WOMAC Pain at Week 26, 0.07 mg SM04690 vs Placebo
- H14. Change in WOMAC Pain at Week 26, 0.03 mg SM04690 vs Placebo
- H15. Change in WOMAC Function at Week 26, 0.07 mg SM04690 vs Placebo
- H16. Change in WOMAC Function at Week 26, 0.03 mg SM04690 vs Placebo
- H17. Change in WOMAC Pain at Week 26, 0.23 mg SM04690 vs Placebo
- H18. Change in WOMAC Function at Week 26, 0.23 mg SM04690 vs Placebo
- H19. Change in Patient Global Assessment at Week 26, 0.07 mg SM04690 vs Placebo
- H20. Change in Patient Global Assessment at Week 26, 0.03 mg SM04690 vs Placebo
- H21. Change in Patient Global Assessment at Week 26, 0.23 mg SM04690 vs Placebo

8.2.2. Subgroup Analysis

The primary and secondary efficacy analysis described above will be further explored by the following covariates:

- KL Grade 2 vs. KL Grade 3
- Age Groups: $\text{age} < 65$, $65 \leq \text{age} < 75$, $\text{age} \geq 75$
- BMI Groups: $\text{BMI} < 30$, $30 \leq \text{BMI} < 35$, $\text{BMI} \geq 35$
- Bilateral knee vs. unilateral knee OA

- WPI: $WPI < 13$, $WPI \geq 13$

Each covariate will be added to the original ANCOVA model along with a term for the interaction between treatment group and the covariate at Week 13 for WOMAC pain, WOMAC function and Patient Global, and Week 26 for medial JSW. The significance of each interaction term will be determined using a likelihood ratio test that compares the original model to the model with the interaction. If the significance level of the interaction is $P < 0.10$ at Week 13 for WOMAC pain, WOMAC function and Patient Global, and Week 26 for medial JSW, the interaction model will be evaluated at those timepoints as well as subsequent timepoints.

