4.2. Exclusion Criteria

Any potential subject who meets one or more of the following criteria will not be included in this study:

1. Women who are pregnant or lactating
2. Women of childbearing potential (i.e., who are not surgically sterile or postmenopausal as defined by no menstrual periods for 12 consecutive months and no other biological or

physiological cause for amenorrhea can be identified); males who are sexually active and have a partner who is capable of becoming pregnant, neither of which have had surgery to become sterilized, who are not using an effective method of birth control (e.g., surgically-implanted hormonal therapy, intrauterine devices or oral birth control with barrier method)

3. Body mass index (BMI) >40
4. Partial or complete joint replacement in the target knee
5. Previous exposure to SM04690
6. Major surgery (e.g., interventional arthroscopy) in the target knee within 52 weeks prior to any study injection
7. Any planned or elective surgery during the study period
8. Significant and clinically evident misalignment of the target knee that would impact subject function, as determined by the Investigator
9. History of malignancy within the last 5 years; however, subjects with prior history of in situ cancer or basal or squamous cell skin cancer are eligible. Subjects with other malignancies are eligible if they have been continuously disease free for at least 5 years prior to any study injection
10. Clinically significant abnormal Screening Visit hematology values, blood chemistry values, HbA1c, or urinalysis values as determined by the investigator
11. Any condition, including laboratory findings (not included in the Screening Visit laboratory tests) and findings in the medical history or in the pre-study assessments, that, in the opinion of the Investigator, constitutes a risk or contraindication for participation in the study or that could interfere with the study objectives, conduct, or evaluation
12. Comorbid conditions that could affect pain assessment of the target knee, including, but not limited to, inflammatory rheumatic conditions such as rheumatoid arthritis, psoriatic arthritis, systemic lupus erythematosus, diabetic neuropathy, pseudogout, gout, and fibromyalgia
13. Other conditions that, in the opinion of the Investigator, could affect pain assessment of the target knee, including, but not limited to, symptomatic hip osteoarthritis and symptomatic degenerative disc disease

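### SAP 8.2.2 tests treatment interaction with age, BMI and WPI only in coarse groups, which costs power at the exploratory P<0.10 gate if effect modification is roughly linear

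*SAP*

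**What the plan says.** SAP 8.2.2 introduces the analysis as exploratory: "The primary and secondary efficacy analysis described above will be further explored by the following covariates". The list has five covariates. Two are binary (KL grade 2 or 3; bilateral or unilateral OA). The other three are cut into groups:

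- age: under 65, 65 to under 75, 75 and over
- BMI: under 30, 30 to under 35, 35 and over
- WPI: under 13, 13 and over

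For each covariate, "Each covariate will be added to the original ANCOVA model along with a term for the interaction between treatment group and the covariate". The outcomes are WOMAC pain, WOMAC function and Patient Global at Week 13, and medial JSW at Week 26. Significance is "determined using a likelihood ratio test that compares the original model to the model with the interaction". If P is below 0.10, the interaction model is evaluated at that visit and later ones. No continuous version is planned.

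All three variables exist as numbers: date of birth (Protocol 6.1), height and weight (Protocol 5.4.3), and a WPI score (Protocol 5.7; SAP 6.2). The Protocol enrols ages 40 to 80 (4.1), excludes BMI above 40, and excludes comorbid conditions that include "diabetic neuropathy, pseudogout, gout, and fibromyalgia" (4.2). Neither document gives an expected distribution of age, BMI or WPI, a subgroup size, or the power of any interaction test.

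**The concern.** With three doses and placebo, a three-level factor has (3-1) x 3 = 6 interaction df. A linear term or a two-level factor has 3. Grouping discards the variation within each group, and for age and BMI it also doubles the df. Some groups may be thin: the cap at 80 leaves a narrow band for age 75 and over, and the fibromyalgia exclusion suggests that high WPI scores are uncommon.

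The gate decides what happens next. A graded effect that it misses is not followed to later visits, and finding such effects is the purpose of this analysis.

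**Working it through.** **1. The plan's own figure.** None exists for interactions. The nearest is the 95.8% main-effect power for WOMAC pain (SAP 2.1). The model described there has difference 5.8 - 3.5 = 2.3, residual SD 4 x sqrt(1 - 0.1^2) = 3.98, and SE 3.98 x sqrt(2/100) = 0.563. Then 2.3/0.563 = 4.09, and two-sided power at 5% is Phi(4.09 - 1.96) = 98.3%. The stated figure is not reproduced, but nothing below depends on it.

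**2. Inputs.** From the documents: N = 445 in four equal arms (about 111 each), the cut points, the 0.10 level, ages 40-80 and BMI up to 40. Assumed: the covariate distributions, and a linear change in dose effect.

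**3. Method.** Information kept by grouping is k = between-group variance / total variance of the covariate. Power comes from the noncentral F distribution at 0.10. The effect is sized so that the continuous test (3 and 436 df) has 80% power, which needs noncentrality 8.86. The grouped test has noncentrality k x 8.86, with 6 and 432 df for three groups or 3 and 436 for two.

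*k by hand, age uniform on 40-80.* Shares are 0.625, 0.25 and 0.125; group means 52.5, 70 and 77.5; overall mean 60. Between-group variance = 0.625 x 56.25 + 0.25 x 100 + 0.125 x 306.25 = 98.4. Total = 40^2/12 = 133.3. So k = 0.74.

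*k for WPI with a normal underlying score.* For upper share s cut at z, k = phi(z)^2 / [s(1-s)]. At s = 0.10, k = 0.1755^2/0.09 = 0.342.

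**4. Results against an 80% continuous test.** Loss = (80 - grouped power)/80.

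| Covariate, assumed distribution | Share in top group | k | Grouped power | Loss |
|---|---|---|---|---|
| Age, mean 55, SD 8 | 0.5% | 0.39 | 35% | 57% |
| Age 60/9 | 3.6% | 0.61 | 49% | 39% |
| Age 65/8 | 7.8% | 0.73 | 56% | 30% |
| Age uniform | 12.5% | 0.74 | 56% | 30% |
| BMI 28/4.5 | 5.7% | 0.67 | 52% | 35% |
| BMI 30/5 | 14% | 0.77 | 58% | 28% |
| BMI 32/5 | 23% | 0.82 | 61% | 24% |
| WPI, normal score | 5% | 0.22 | 29% | 63% |
| WPI, normal score | 10% | 0.34 | 39% | 51% |
| WPI, normal score | 20% | 0.49 | 51% | 36% |
| WPI, normal score | 50% | 0.64 | 61% | 23% |

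Right-skewed (negative binomial) WPI scores with means 3, 5, 7 and 9 put 0.8%, 6%, 15% and 25% at 13 or more, and lose 72%, 42%, 26% and 19%.

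**5. Benchmark.** If the continuous test has 60% power (noncentrality 5.45), the losses are 36-59% for age and 30-40% for BMI. Against a 90% test they are 23-52% and 18-28%. The relative loss grows as power falls.

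**6. Thin groups.** At 111 per arm, age 75 and over is about 1 to 9 subjects per arm under the bell-shaped assumptions and 14 if age is uniform. WPI of 13 or more at a 5-10% share is 6 to 11 per arm. BMI is reasonably spread (51/35/14% at mean 30, SD 5).

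**7. Which models are compared.** The ANCOVA in SAP 8.1.1 adjusts for baseline and does not contain the subgroup covariate. Read literally, the likelihood ratio test therefore covers main effect and interaction together: 2 + 6 = 8 df for three groups, 1 + 3 = 4 df for two groups or a linear term. In simulation with no interaction and an assumed prognostic effect of 0.15 SD per SD of the covariate, this comparison opens the gate 48-59% of the time with the age or BMI groups and about 80% with continuous terms. A test of the interaction terms alone holds about 10% either way.

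**The case against.** The strongest reply is that the result depends on a linear gradient. If the effect steps at age 65, with a two-group split sized to 80% power, the SAP's three groups have about 70% and a linear term 54-60%. This stands, so the groups should stay as a check.

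Part of the age and BMI loss is also the price of df. A flexible continuous term with 6 interaction df would have about 70% power, not 80%. Against that, the groups still lose (70 - 49)/70 = 30% for age 60/9 and (70 - 58)/70 = 17% for BMI 30/5. The gap narrows but remains.

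Third, the distributions are assumed. The fibromyalgia criterion excludes a condition, not a score, and no eligibility criterion sets a WPI limit. A low share at 13 or more is therefore an inference, and the WPI range is wide for that reason.

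Finally, the analysis lies outside the H1-H21 hierarchy and the Protocol (10.5.4) rules out adaptation. This limits the consequence but does not make the grouped test the better screen.

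**Conclusion.** The point holds in a limited form. Under roughly linear effect modification, testing only in groups loses about a quarter to two-fifths of the power for BMI, about 30-60% for age and about 23-70% for WPI; the most extreme WPI assumptions fall slightly outside that range. The sizes rest on assumed distributions and on a continuous test with 60-80% power.

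A reader might infer four stronger things that the documents do not support:

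- **That every covariate loses at least a third, through very unequal groups.** BMI often loses less and is fairly balanced. Inequality is likely for age 75 and over, and only inferred for WPI.
- **That the gate will usually miss a real gradient.** For the literal comparison this depends on the main effect. With one dose's effect changing by 0.25 SD per SD of the covariate, the grouped gate opens 38% (age) and 47% (BMI) of the time with no main effect, and 87% and 94% with a main effect of +0.15, partly for the wrong reason.
- **That a non-significant interaction will be reported as consistency across patients.** Neither document says so.
- **That the confirmatory results are affected.** They are not.

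**What to change.** In SAP 8.2.2, for age, BMI and WPI:

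- Run the P<0.10 gate with a continuous covariate-by-treatment interaction: one slope per dose, 3 df.
- State the comparison explicitly: the model with covariate main effect plus interaction against the model with the covariate main effect only. Without this, moving to continuous terms makes false opening by a prognostic covariate more frequent (step 7). The same wording should apply to KL grade and bilateral OA, which share the test.
- Keep the listed groups to display subgroup estimates and as a check for non-linear or step patterns.

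The cost is a few sentences in the SAP, with no new data. The downside is lower power than the groups if the effect changes abruptly at a cut point.

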10.5.5. Efficacy Analysis

Efficacy analysis will be performed on the ITT, mITT, and PP Analysis Sets. Change in primary and secondary efficacy endpoints from baseline will be estimated at specified time points using parametric analysis of covariance (ANCOVA) models. Formal hypothesis testing between treatment groups will be conducted using a strategy to control the familywise error rate; the error rate strategy is detailed in the study's SAP.

Exploratory efficacy analysis will be performed on the ITT, mITT, and PP analysis sets. Change in WOMAC total, WOMAC pain subscore, WOMAC function subscore, Patient Global Assessment, Physician Global Assessment, JSW and HRQOL from baseline will be estimated at specified time points using parametric analysis of covariance (ANCOVA) models. Logistic regression will be used to analyze the proportion of OARSI responders within each treatment group compared to placebo at specified time points. Exploratory subgroup analyses may also be performed.

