5.2. Handling of Missing Data

Multiple imputation will be utilized for the primary and secondary analyses. Missing data will be imputed based upon the observed data for each outcome under the missing at random (MAR) assumption following the paradigm first developed by Rubin (Schafer 1999). The imputation will adjust for the outcome’s baseline data in a regression model with data imputed independently for each timepoint; any missing baseline data will also be imputed. A total of 10 imputation datasets will be created and analyzed based upon accepted convention (Schafer 1999). Error estimates of the multiple imputation itself as well as an overall summary of the efficacy analysis will be averaged across the 10 imputed datasets based upon Rubin’s paradigm.

Specifically, let Q denote the imputed mean of an efficacy outcome Y subject to missing data at a given timepoint, where the estimate of that mean for any i^{th} imputation would be defined as function of both observed and missing data such that

$$\widehat{Q}^{(i)} = E\left(Q^{(i)} | Y_{observed}, Y_{missing}^{(i)}, Y_{Baseline}, I(Group)\right), i = 1, \dots, 10.$$

After all 10 datasets have been imputed, the overall estimate of Q is a simple average defined as

$$\bar{Q} = \frac{\sum_{i=1}^{10} \widehat{Q}^{(i)}}{10}.$$

For this analysis using 10 imputed datasets, the variance of \bar{Q} is defined as

$$Var(\bar{Q}) = 1.1B + \bar{U}$$

where B is the between imputation variance and U is the within imputation variance:

$$B = \frac{1}{9} \sum_{i=1}^{10} (\widehat{Q}^{(i)} - \bar{Q})^2;$$

$$\bar{U} = \frac{\sum_{i=1}^{10} U^{(i)}}{10}.$$

Imputations will be performed with a seed of 201610141.

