8.1.1. ANCOVA Model for Continuous Efficacy Outcomes

ANCOVA models will be used for all continuous efficacy outcome measures summarized by change from baseline in order to test the following three hypotheses:

$$H_0: (\beta_i - \beta_0) = 0$$

$$H_A: (\beta_i - \beta_0) \neq 0, \text{ where } i = 1,2,3$$

In the statement above, β is the least squares estimate in the change in the continuous efficacy outcome from baseline at each timepoint (where β_0 is the estimate for placebo), and i represents each of the three SM04690 treatment groups.

Least squares estimate of difference between each treatment group and placebo in the change in the continuous efficacy outcome from baseline at each timepoint, adjusted for baseline value, will be reported along with unadjusted 95% confidence intervals and P values.

Continuous efficacy measures to be analyzed by the ANCOVA model include:

- WOMAC Pain
- WOMAC Function
- WOMAC Total
- Patient Global Assessment
- Physician Global Assessment
- Medial and Lateral Joint Space Width
- SF-36

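### SAP 8.2.2 takes the interaction P value from a joint test of main effect and interaction, so a purely prognostic covariate can open the P<0.10 gate far more than 10% of the time

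*SAP*

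**What the plan says.** SAP 8.2.2 lists five covariates. KL grade, bilateral versus unilateral OA and WPI have two levels; age and BMI have three. The modelling step is: "Each covariate will be added to the original ANCOVA model along with a term for the interaction between treatment group and the covariate". This is done at Week 13 for WOMAC pain, WOMAC function and Patient Global, and at Week 26 for medial JSW. The significance of each interaction term is then "determined using a likelihood ratio test that compares the original model to the model with the interaction". If that P value is below 0.10, "the interaction model will be evaluated at those timepoints as well as subsequent timepoints".

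The original model is the one in SAP 8.1.1. It estimates each dose-versus-placebo difference "in the change in the continuous efficacy outcome from baseline at each timepoint, adjusted for baseline value", so it contains arm and baseline and no subgroup covariate.

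Neither document names a reduced model that includes the covariate's main effect, and neither states degrees of freedom for the test. Protocol 10.5.5 says only: "Exploratory subgroup analyses may also be performed".

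**The concern.** A likelihood ratio test assesses every term by which its two models differ. Here those terms are the covariate's main effect and its interaction with arm. The SAP labels the result as the significance of the interaction alone.

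A subgroup factor may well predict change in pain, function or joint space whatever the treatment. Under the stated comparison, that prognostic effect alone can bring the P value below 0.10 when the treatment effect is identical in every subgroup. A P value reported as an interaction test could then be read as evidence that some patients respond better to SM04690. The gate is also the plan's only stated rule for which interaction models are carried to later timepoints.

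**Working it through.** **Inputs from the documents**

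- N of about 445 in four arms, 1:1:1:1 (SAP 2.1).
- Gate at P<0.10; three two-level and two three-level covariates; four outcomes (SAP 8.2.2).
- Original model: arm + baseline value (SAP 8.1.1).

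The plan states a threshold but no pass rate, so there is no figure of its own to reproduce.

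**Inputs assumed.** The documents give neither prognostic effects nor subgroup prevalences. I took a prognostic effect *d* of 0 to 0.5 residual SD beyond baseline, two-level prevalence of 10% to 50%, and two three-level splits.

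**Step 1: degrees of freedom.** With four arms, each covariate df brings 3 interaction df.

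| Covariate | Main effect | Interaction | Stated comparison |
|---|---|---|---|
| Two-level | 1 | 3 | 4 |
| Three-level | 2 | 6 | 8 |

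**Step 2: pass rate of the stated test with no true interaction.** It is P(noncentral χ²(df, λ) > 0.90 quantile of χ²(df)). The critical value is 7.779 on 4 df and 13.362 on 8 df.

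- Two levels: λ = N·p(1−p)·d². For p = 0.5 and d = 0.2, λ = 445 × 0.25 × 0.04 = 4.45, and the pass rate is 48.1%.
- Three levels, linear, with *d* spanning the whole range: λ = N·Var(covariate effect). In equal thirds the variance is d²/6. For d = 0.2, λ = 445 × 0.04/6 = 2.97, and the pass rate is 28.2%.

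| Pass rate (%) at d = | 0 | 0.05 | 0.1 | 0.2 | 0.3 | 0.5 |
|---|---|---|---|---|---|---|
| Two-level, 50% | 10 | 12.2 | 19.2 | 48.1 | 81.3 | 99.8 |
| Two-level, 20% | 10 | 11.4 | 15.8 | 34.5 | 62.5 | 96.9 |
| Two-level, 10% | 10 | 10.8 | 13.2 | 23.5 | 41.1 | 81.3 |
| Three-level, equal thirds | 10 | 11.0 | 14.1 | 28.2 | 52.7 | 93.8 |
| Three-level, 55/33/12 | 10 | 10.7 | 12.9 | 22.9 | 41.0 | 83.7 |

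**Step 3: simulation check.** Four-arm ANCOVA, 111 per arm, 4000 replicates, LRT statistic = N·ln(RSS small / RSS full). For a 50/50 covariate at d = 0 / 0.1 / 0.2 / 0.3 / 0.5, the stated comparison passed in 10.7 / 19.5 / 48.6 / 81.2 / 99.6% of trials. Comparing a main-effects model with the full model gave 10.0% at every *d*. That correct comparison gave 10.5% at 20% prevalence and 11.4% for a 50/35/15 three-level split. The small excess comes from using the χ² approximation in finite samples.

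**Step 4: how many openings reflect an interaction signal.** For a 50/50 covariate I drew the main-effect part (noncentral, 1 df) and the interaction part (central, 3 df) independently, 2,000,000 times. Of the tests passing the stated gate, the share that would also pass the correct 3-df test is 70 / 60 / 42 / 20 / 12 / 10% at d = 0 / 0.05 / 0.1 / 0.2 / 0.3 / 0.5.

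**Step 5: all gates.** There are 5 covariates × 4 outcomes = 20 gates: 12 two-level and 8 three-level. With no prognostic effect, 20 × 0.10 = 2.0 false openings are expected. With 50/50 and equal-thirds splits and every covariate prognostic for every outcome:

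- d = 0.1: 12 × 0.192 + 8 × 0.141 = 3.4
- d = 0.2: 12 × 0.481 + 8 × 0.282 = 8.0

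**Step 6: loss of power.** When there is a real interaction and no main effect, the extra df dilute the test. At λ = 6, power at the 0.10 level is 60% on 4 df against 64% on 3 df, and 49% on 8 df against 53% on 6 df.

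**The case against.** The strongest reply is that this is loose wording. SAP 8.2.2 twice names the interaction as the thing being tested, and a competent programmer would probably fit the main-effects model as the comparator. That may well have been the intent. But the sentence before the test uses the same term, original, for the model before the covariate is added, so this reading replaces the comparison that the SAP specifies. A pre-specified test should not depend on that.

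The second reply is that little hangs on it, and most of this stands. The analysis is exploratory, the interim analysis leads to no adaptation (SAP 5.1), and the interaction model, once triggered, still estimates main effect and interaction separately. About 2 of 20 gates would open by chance even under the correct test.

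The third reply is that the size rests on assumptions, and that the 20-gate totals lean high. That is fair. Taking WPI ≥13 at 10% prevalence and 55/33/12 splits for age and BMI (also assumptions), the totals fall to 3.1 at 0.1 SD and 6.6 at 0.2 SD. If in addition only half the covariate–outcome pairs are prognostic, they are 2.5 and 4.3. All remain above 2.0.

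**Conclusion.** The concern holds. As written, the rule is a 4- or 8-df joint test presented as an interaction test. Its false-pass rate is about 10% only when the covariate has no prognostic effect beyond baseline. At an assumed 0.1 to 0.3 SD it ranges from 13% to 81% over the prevalences and splits considered.

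The direction follows from the text; the size depends on effects and prevalences that the documents do not give. The primary analysis and the H1–H21 hierarchy in SAP 8.2.1 are unaffected. It should be fixed because the specification is definitely wrong and the correction is almost free, although the reach is limited to exploratory subgroup findings.

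**What to change.** In SAP 8.2.2, define the reduced model as arm + baseline value + subgroup covariate, and the full model as that plus arm-by-covariate. Test on the interaction df only (3 for two-level covariates, 6 for age and BMI) and keep P<0.10.

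A related point needs settling whichever comparison is used. SAP 5.2 says "Multiple imputation will be utilized for the primary and secondary analyses" but gives a combining rule only for a single mean. If the subgroup test is run on the 10 imputed datasets, the SAP should name a standard pooled multi-df test of the interaction terms.

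The cost is one sentence in 8.2.2, one changed reduced model in the program, and one sentence on pooling if it applies. No other analysis is affected.

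### If the subgroup interaction tests use the SAP's multiply imputed data, as the text implies, interaction estimates shrink by about the missing fraction, because the imputation model omits the subgroup factors

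*SAP*

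**What the plan says.** **Imputation (SAP 5.2).** "Multiple imputation will be utilized for the primary and secondary analyses". Each outcome is imputed from its own "baseline data in a regression model with data imputed independently for each timepoint", and the formula conditions on the observed outcome, its baseline and the treatment group. "A total of 10 imputation datasets will be created and analyzed based upon accepted convention". The pooling formulas are Rubin's rules for a mean and its variance.

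**Subgroups (SAP 8.2.2).** "The primary and secondary efficacy analysis described above will be further explored by the following covariates": KL grade, age group, BMI group, bilateral versus unilateral OA, and WPI. "Each covariate will be added to the original ANCOVA model along with a term for the interaction between treatment group and the covariate". Significance comes from a "likelihood ratio test that compares the original model to the model with the interaction", with a threshold of 0.10. The gate applies at Week 13 for WOMAC pain, WOMAC function and Patient Global, and at Week 26 for medial JSW. Passing it means that the interaction model is evaluated there and at later visits.

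**Link between the two.** SAP 8 runs all efficacy analysis on the ITT set, and SAP 5.4 sends missing visits to section 5.2. No section says outright which data the subgroup models use.

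**The concern.** None of the five subgroup factors, and no interaction of a factor with treatment, is in the imputation model. Each imputed value is therefore drawn as if the treatment effect were the same in every subgroup. Using such values to test whether the effect differs pulls the estimate toward no difference. That bias is in the estimate, so no pooling rule removes it.

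The gate decides whether subgroup results are looked at further, and SAP 8.3 says the interim efficacy analyses are not repeated. A missed modifier therefore gets no planned second look at the same visits. A finding of no interaction for KL grade, bilateral disease or WPI could carry into the choice of population for later trials.

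**Working it through.** **Inputs from the documents.** 445 subjects randomized 1:1:1:1, so 445/4 = 111.25 per arm; baseline–final correlation 0.1 (SAP 2.1); 10 imputations (SAP 5.2); gate level 0.10 (SAP 8.2.2).

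**Assumptions.** A two-level factor split 50:50; one dose differing by 0.60 SD between levels; outcomes missing completely at random. The missing fraction d is not stated, so the range is 5 to 20%. SAP 2.1 uses 100 per group in its power simulation, and 1 − 100/111.25 = 10.1%, but the SAP does not call this a dropout allowance.

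**Step 1, stated level.** On complete data with no main effect and no interaction, 3,000 simulated trials reject 10.2% of the time for the interaction-only test (3 df). For the test as worded (4 df) it is 10.8%. The stated 0.10 is reproduced.

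**Step 2, shrinkage.** The observed share (1 − d) carries the interaction and the imputed share d carries none, so the expected estimate is (1 − d) × 0.60. This gives 0.57, 0.54 and 0.48 at 5, 10 and 20% missing. Simulation gives 0.579, 0.539 and 0.477.

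**Step 3, level of an interaction-only test under Rubin-type pooling.** Let V be the complete-data variance of the interaction estimate.
- True variance of the pooled estimate: V(1 − d + d/10).
- Variance reported by Rubin's rules: V(1 + 1.1d).
- Ratio at d = 0.10: 0.91/1.11 = 0.820.
- The 10% critical value of chi-square on 3 df is 6.251, so the effective cut-off is 6.251/0.820 = 7.63, with tail probability 0.054.

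The same steps give ratios 0.905 and 0.672, and levels 0.075 and 0.026, at 5 and 20% missing.

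**Step 4, power.** With 111 per arm, the variance of the between-level difference within one arm is 4/111 = 0.0360 in SD² units. The 3-df non-centrality is 0.60² × (3/4)/0.0360 = 7.49, which gives 74% power on complete data. Under the plan's imputation it becomes (1 − d)² × 7.49/(1 − d + d/10), judged against the Step 3 cut-off. That is 66, 58 and 40% at 5, 10 and 20% missing.

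Simulation (10 imputations, pooled 3-df Wald test):

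| Missing | Level, plan | Level, factor imputed | Power, plan | Power, factor imputed | Power, observed cases |
|---|---|---|---|---|---|
| 5% | 0.075 | 0.101 | 67% | 72% | 73% |
| 10% | 0.058 | 0.096 | 57% | 69% | 70% |
| 20% | 0.020 | 0.098 | 38% | 62% | 64% |

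A repeat simulation gave power of 67, 56 and 37% against 70, 67 and 61%, within 2.5 points of the table. For a three-level factor the plan's level is 0.045 at 10% missing and 0.019 at 20%.

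**Step 5, the test as worded.** The reference model has no subgroup covariate, so the test takes in the main effect as well: 1 + 3 = 4 df for a two-level factor, 2 + 6 = 8 for a three-level one. With no interaction, 10% missing and a pooled likelihood ratio test, the gate opens with probability 0.052, 0.102, 0.308 and 0.642 for main effects of 0, 0.1, 0.2 and 0.3 SD. Repairing the imputation alone leaves 0.44 at 0.2 SD.

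**Step 6, other pooling.** For the interaction-only test at 10% missing, averaging the likelihood ratio statistics gives a level of 0.088, averaging P values gives 0.073, and one completed dataset gives 0.105.

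**The case against.** The SAP never says that the subgroup models use imputed data. Multiple imputation is assigned to the primary and secondary analyses, and 8.2.2 is a separate exploration of them. The absence of a pooling rule fits a single fit to observed cases equally well, and on that reading nothing shrinks. This stands as a limit on certainty. Still, 8.2.2 extends the ANCOVA already described, on the ITT set, and no section mentions observed cases, so imputed data remain the natural reading.

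A reader might infer that the gate as written runs well below 10%. The documents do not support that. The low levels need an interaction-only comparison and Rubin-type pooling. The quoted test has neither: its reference model lacks the main effect, so a prognostic factor can push the gate above 10%, and no pooling method is named.

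The missing rate is unknown, and three of the four gated outcomes are at Week 13 after a single injection. At 5% missing the power loss is only about 3 to 5 points. The assumed interaction is also large: 0.60 SD is about the whole pain effect assumed in SAP 2.1, (5.8 − 3.5)/4 = 0.575 SD. For smaller interactions, power is low under any method. Both remarks are fair. They limit the practical damage but do not change the proportional shrinkage.

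Finally, Protocol 10.5.5 treats subgroup analyses as exploratory and optional, and no adaptation follows from the interim analysis. That stands too.

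**Conclusion.** The point holds, conditional on the subgroup models using the data imputed under SAP 5.2. Interaction estimates are then attenuated by about the missing fraction when missingness is unrelated to the factor. For a 0.60 SD interaction with 111 per arm, an interaction-only test loses about 3, 11 and 24 percentage points of power at 5, 10 and 20% missing (70 − 67, 67 − 56, 61 − 37). If that test is pooled by Rubin-type rules, its null level is about 0.075, 0.06 and 0.02 instead of 0.10. These levels do not describe the likelihood ratio test as worded, whose error can go either way. Separately, the SAP has no rule for combining likelihood ratio tests over 10 datasets.

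It would be wrong to infer that the efficacy conclusions are at risk. The subgroup analyses lie outside H1–H21, and the primary result is unaffected. The change is worth making because it is cheap and the gate governs what is examined further.

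**What to change.** In SAP 8.2.2:

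1. State which data the subgroup models use. Either re-impute the outcome for each subgroup analysis with that factor and its treatment interaction in the imputation model (or impute within factor levels), or use observed cases.
2. Test the interaction terms only, against a model that already contains the factor's main effect.
3. Name the test: a pooled multi-parameter Wald F test under Rubin's rules for imputed data, or an ordinary F or likelihood ratio test for observed cases.

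Items 1 and 2 are both needed, since neither repairs the other's problem. The cost is a few sentences and one extra imputation run per factor. The larger imputation model will be less stable in sparse levels such as age 75 or over, and observed cases can be used there.
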